10.5 Safety

Safety endpoints include SAEs and AEs ([Appendix 4](#)). Adverse events will be analyzed using quantitative and qualitative measures. Treatment-emergent adverse events will be summarized by treatment group for all AEs, related AEs, serious adverse events, deaths, adverse events leading to discontinuation of study medication or to withdrawal from study, adverse events of different severity and adverse events of different chronicity. Treatment-emergent adverse events will be coded using MedDRA and summarized by system organ class and preferred term for each treatment group. For selected adverse events, time to first event may be visualized using Kaplan-Meier plots and tested between treatment using the log-rank test.

Available laboratory data will be summarized by each visit including change from baseline. The number of normal, abnormal not clinically significant and abnormal clinically significant values on each parameter will be summarized for change over study using shift tables. All data will be listed and values outside reference ranges will be highlighted in the listings.

Vital signs will be summarized by each visit including change from baseline. All data will be listed and values outside reference ranges will be highlighted in the listings.

10.5.1 Missing Data

The patients withdrawn from treatment will be followed up regarding their status according to the 7-point ordinal scale at Day 29 as far as possible (exceptions for patients with withdrawn consent or lost to follow-up) and this data will be the primary source for handling missing data in the study. Status on the 7-point scale, including vital status, will also be collected at the Day 60 follow-up. In survival analysis, patients with death as outcome will be censored at Day 29 (Day 60), unless the required event was reached prior to death. In analyses of oxygen need, patients in ventilator care or with death as outcome will be considered in oxygen need. In analyses of ventilator need, patient with death will be considered in ventilator need. Further details on imputation will be given in the Statistical Analysis Plan.

10.6 Interim Analyses

There will be no formal interim analysis in the study.

11 DATA MONITORING COMMITTEE

Enfentrine has been studied in over 1000 patients with COPD, which is a group known to have severely compromised lung physiology and multiple comorbidities, including in over 600 patients for 4 weeks duration. Because the safety profile in this population has been shown to be similar to placebo over the maximal study duration and expected exposure for this study with a 2 mg twice daily pMDI dose is similar to that expected from a twice daily 3 mg nebulized dose in COPD patients, a formal data safety monitoring board is not planned.

This is a single site study with a small number of patients. Given the potential severity of COVID-19 and limited information about the expected clinical course, a protocol team composed of the Sponsor's Medical Monitor, the Investigator and 2 independent physicians, will review blinded pools of AE data at regular intervals (approximately every 10 patients randomized) to evaluate whether a significant number of unexpected AEs are occurring (AEs that do not fit with the known course of COVID-19).

If there are a significant number of unexpected AEs, the protocol team will be asked to review unblinded safety data in an ad hoc meeting. The committee can recommend dose reduction, or stopping the study for safety or unblinding concerns. The study will not stop enrollment awaiting these reviews, although the protocol team may recommend temporary or permanent cessation of enrollment based on their safety reviews.

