6.4 Emergency Unblinding

The blind will be broken only if specific emergency treatment would require knowing the treatment status of the patient or if the protocol review committee (Section 11) recommends unblinding data for safety review reasons. If the blind needs to be broken for an individual patient, the Investigator will contact the Sponsor as soon as feasible. The Investigator may unblind the study medication immediately if he/she feels it is necessary prior to contacting the Sponsor. However, the Investigator should promptly document and explain to the Sponsor any premature unblinding. Otherwise, all blinding will be maintained until all queries are resolved and the database is locked.

The statistical vendor for this study is the site's data management group and will have access to break the blind, if necessary, but this will be kept in a secure access area.

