6.6 Method of Assigning Patients to Treatment Groups (Randomization)

Randomization will take place prior to the first study medication administration in the order patients are enrolled and in accordance with a computer-generated randomization list supplied by an independent statistician. Available randomization numbers must be used sequentially for the next enrolled patient. Patients will be dosed with either blinded ensifentrine or placebo according to the randomization scheme.

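### Section 11 states no criterion for unblinded review of COVID-like harm, and it would give unblinded data to the Investigator without a firewall

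*Protocol*

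**What the plan says.** Protocol section 11 sets up a protocol team of the Sponsor's Medical Monitor, the Investigator and two independent physicians. About every 10 patients randomized, the team reviews blinded pools of AE data "to evaluate whether a significant number of unexpected AEs are occurring (AEs that do not fit with the known course of COVID-19"). If there are enough such events, "the protocol team will be asked to review unblinded safety data in an ad hoc meeting". The number is not defined. The same section gives as its background the potential severity of the disease and "limited information about the expected clinical course".

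The team has real powers. "The committee can recommend dose reduction, or stopping the study for safety or unblinding concerns", and "the protocol team may recommend temporary or permanent cessation of enrollment based on their safety reviews".

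Protocol section 6.4 is wider. The blind may be broken for emergency treatment or "if the protocol review committee (Section 11) recommends unblinding data for safety review reasons", with no limit on the type of event. SAP section 6.6.3 repeats this. Section 6.4 also says that the statistical vendor is the site's "data management group and will have access to break the blind".

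Protocol section 7.4 states that there are no stopping rules and that oversight by this team takes their place, citing section 11. Section 10.6 plans no formal interim analysis.

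**The concern.** There are two gaps.

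**The trigger.** Invasive ventilation and death are categories 6 and 7 of the trial's own COVID-19 scale (Protocol section 8.1.1, Table 10). Appendix 4 counts expected progression of the disease as an AE, so these events reach the blinded pool. A reviewer can nevertheless judge each of them to fit COVID-19, and then none counts towards the one stated trigger. If ensifentrine made the disease worse, the harm would look like this. The yardstick is also soft, because the section admits that little is known about the expected course.

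**Who is unblinded.** The unblinded data go to the whole team, and no closed session or firewall is described. At this single site the Investigator assesses the causality and intensity of every AE (Appendix 4) and may stop study medication at discretion (section 7.1). If unblinded while patients are still being treated and followed, the Investigator makes those later judgements with knowledge of treatment results or allocations.

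**Working it through.** The plan gives no safety threshold, event rate or power figure, so there is no figure of its own to reproduce. The main check is to set the texts side by side.

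| Point | Section 11 | Elsewhere |
|---|---|---|
| Events that can lead to unblinded review | AEs unlike COVID-19, in sufficient number | Section 6.4 and SAP 6.6.3: any safety review reason, no criterion |
| Are deaths and ventilation in the pool? | AE data, blinded | Appendix 4: yes, disease progression is an AE |
| What replaces stopping rules? | This team's review | Section 7.4: refers to section 11 |
| Who sees unblinded data? | The protocol team, including the Investigator | Section 6.4: blind otherwise kept to database lock |
| By patient or by arm? | Not stated | Not stated |

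What the Investigator's judgements feed:

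- Causality feeds the related-AE summaries (SAP Tables 14.3.5 and 14.3.8).
- Severity and stopping of study medication feed the composite of death, SAE, severe AE or early stopping of treatment, which SAP section 9.5 compares between arms.

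**Illustrative arithmetic.** All event rates below are assumptions. With 2:1 allocation, 40 × 2/3 = 26.7, so take 27 ensifentrine and 13 placebo patients at the fourth review. Let pP be the placebo rate (equal to background) and pE the ensifentrine rate.

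- Expected events with harm = 27·pE + 13·pP; without harm = 40·pP.
- P(total ≥ c) = Σ over t ≥ c, Σ over a, of Bin(a; 27, pE) × Bin(t − a; 13, pP). The cut-off c is the smallest count with probability at most 5% without harm.
- By-arm power: the same binomial probabilities summed over all 2×2 tables with one-sided Fisher p ≤ 0.05.

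| pP → pE | Expected, harm v none | c | P(≥ c) without harm | P(≥ c) with harm | By-arm Fisher power |
|---|---|---|---|---|---|
| 5% → 12.5% | 3.375 + 0.65 = 4.03 v 2.0 | 5 | 4.8% | 38% | 2% |
| 10% → 25% | 6.75 + 1.3 = 8.05 v 4.0 | 8 | 4.2% | 57% | 16% |
| 20% → 35% | 9.45 + 2.6 = 12.05 v 8.0 | 13 | 4.3% | 43% | 14% |
| 20% → 50% | 13.5 + 2.6 = 16.1 v 8.0 | 13 | 4.3% | 89% | 45% |

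Two limits on this table:

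- The pooled cut-off works only if the background is known. If it is really 15% and not 10%, with no harm, 8 or more events in 40 has probability 24%, not 4.2%.
- Earlier looks are weaker. At the first review (10 × 2/3 = 6.7, so 7:3), the pooled rule built the same way catches 13%, 16% and 39% for the last three rows, and by-arm Fisher power is 0.1%, 0.5% and 3.2%.

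The blinded pool can therefore hint at a problem late in enrollment if the background is roughly known, but only if disease-like events count. A by-arm look informs judgement and is not a usable test.

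**The case against.** The strongest reply is that the plan already covers this. Section 6.4 and SAP 6.6.3 allow unblinding for safety reasons of any kind, section 11 allows the team to recommend halting enrollment on its safety reviews, and section 7.4 lists serious or unacceptable risk as a ground for termination. SAEs reach the Sponsor within 24 hours (section 8.6.1), and a patient who needs mechanical ventilation comes off study medication (section 7.1.1). This stands in large part. A reader might infer that COVID-like harm can never lead to an unblinded look; the documents do not support that. What survives is narrower: these provisions give authority or handle single patients, and none states a criterion for looking at an excess of disease-like events unblinded.

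The trigger could also be read to include an excess in frequency or severity, since too many deaths might not fit the known course. That reading is open, which is a reason to write it down.

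Three other inferences go too far:

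- That the Investigator would know later patients' allocations. Section 11 does not say whether the data are by patient or by arm, and by-arm totals do not reveal an individual assignment. The extent of unblinding is uncertain.
- That biased causality ratings would distort the composite. Causality is not one of its components; severity and stopping of treatment are.
- That Amendment 2.0 widened AE collection and section 11 was overlooked. Section 11 reviews AE data, so the pool widened automatically.

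Finally, section 11 justifies having no monitoring board: over 1000 COPD patients studied, over 600 of them for 4 weeks, with a safety profile similar to placebo, and a small single-site trial. That is a reasonable case against a formal board. It does not bear on which events should prompt the review already planned, or on who should attend it.

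**Conclusion.** The point holds as an inexpensive improvement. Section 11 is narrower than section 6.4, although section 7.4 leans on it in place of stopping rules, and it provides no protection for the Investigator's blind if the ad hoc review takes place. The effect on the blind is conditional, because the meeting may never be called.

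The conclusion rests on the wording and not on the calculations. Every event rate is assumed, the pooled signal depends on a known background, and by-arm power at 40 patients runs from 2% to 45% across the four scenarios. The argument is for better-directed judgement and a protected blind; it is not a claim that harm would be detected. It also does not mean that the reported safety results are biased, since nothing in the documents shows that an unblinded review was held.

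**What to change.** In section 11:

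1. State that concern about any deaths, SAEs or AEs leading to stopping of study medication (ventilation included), whether or not they resemble COVID-19, can prompt the ad hoc unblinded review. This brings section 11 into line with section 6.4.
2. Limit that review to the two independent physicians. The Investigator and the Medical Monitor receive only the recommendation.
3. Name who prepares the by-arm counts: a statistician confirmed to be separate from the Investigator and site study staff, or the site's data management group under a written firewall. SAP section 6.6 mentions a "computer-generated randomization list supplied by an independent statistician", but neither document shows that this person is separate from the site's data management group, so the separation has to be confirmed.

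The cost is a few sentences and a firewall document, using people and data already in place. No efficacy test is added, so no alpha is spent. The downsides are that the review may be called more often, that small by-arm counts (about 7:3 at the first review) carry some risk of leakage, and that formal power stays low. The trigger remains a judgement without a numerical threshold.

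The change helps only while patients are being enrolled. The SAP's table shells (section 14, Table 14.1.1) already show 45 enrolled. If enrollment is complete, the report should state whether an unblinded review was held and who saw the data, and the wording should be carried into any successor protocol.

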
Number of Patients

Approximately 45 randomized patients are planned.

Treatment Groups and Duration

Every patient enrolled will receive UAB's SoC treatment for COVID-19 infection.

Upon enrollment, patients will be randomized 2:1 to receive blinded ensifentrine via pMDI BID + SoC or placebo pMDI BID + SoC over 29 days or until discharge from hospital, whichever is first.

- Treatment Arm 1 (n=30): Blinded ensifentrine (2 mg) pMDI BID + Standard of Care treatment for COVID-19 infection
- Treatment Arm 2 (n=15): Blinded placebo pMDI BID + Standard of Care treatment for COVID-19 infection

Statistical Methods

[figure not shown]
All analyses are considered exploratory and hypothesis-generating.

Sample Size

This is a pilot study and it is not formally powered based on any specific endpoint. Sample size has been set to minimize the number of patients exposed, but still large enough to give reliable estimates on the efficacy and safety of ensifentrine in the target population.

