- It is **not** acceptable for the Investigator to send photocopies of the patient's medical records to Sponsor/Sponsor's designee in lieu of completion of the Verona Pharma /AE/SAE eCRF page.
- There may be instances when copies of medical records for certain cases are requested by groups such as the Sponsor/Sponsor's designee, Health Authority, or Ethics Committee. In this case, all patient identifiers, with the exception of the subject/patient number, will be redacted on the copies of the medical records before submission to records to the Sponsor/Sponsor's designee.

The Investigator will attempt to establish a diagnosis of the event based on signs, symptoms, and/or other clinical information. Whenever possible, the diagnosis (not the individual signs/symptoms) will be documented as the AE/SAE.

Assessment of Intensity

The Investigator will make an assessment of intensity for each AE and SAE reported during the study and assign it to one of the following categories:

For AEs not included in the protocol defined grading system, the following guidelines will be used to describe severity.

Mild: An event that is easily tolerated by the patient, causing minimal discomfort and not interfering with everyday activities.

- **Grade 1:** Events that are usually transient and may require only minimal or no treatment or therapeutic intervention and generally do not interfere with the subject's usual activities of daily living.

Moderate: An event that causes sufficient discomfort and interferes with normal everyday activities.

- **Grade 2:** Events that are usually alleviated with additional specific therapeutic intervention. The event interferes with usual activities of daily living, causing discomfort but poses no significant or permanent risk of harm to the research subject.

Severe: An event that prevents normal everyday activities. An AE that is assessed as severe should not be confused with a SAE. Severe is a category utilized for rating the intensity of an event; and both AEs and SAEs can be assessed as severe.

- **Grade 3:** Events interrupt usual activities of daily living, or significantly affects clinical status, or may require intensive therapeutic intervention. Severe events are usually incapacitating.
- **Grade 4:** Events that are potentially life threatening.

An event is defined as ‘serious’ when it meets at least one of the predefined outcomes as described in the definition of an SAE, NOT when it is rated as severe.

Assessment of Chronicity

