6.6.3 Blinding

The UAB IDS Pharmacy's unblinded pharmacist will label the study medication and perform accountability measures.

The blind will be broken only if specific emergency treatment would require knowing the treatment status of the patient or if the protocol review committee recommends unblinding data for safety review reasons. If the blind needs to be broken for an individual patient, the Investigator will contact the Sponsor as soon as feasible. The Investigator may unblind the study medication immediately if he/she feels it is necessary prior to contacting the Sponsor. However, the Investigator should promptly document and explain to the Sponsor any premature unblinding. Otherwise, all blinding will be maintained until all queries are resolved and the database is locked.

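### If the ad hoc safety review is triggered, the only site's Investigator and the Sponsor's Medical Monitor see unblinded data, which could weaken blinded judgment of the Investigator-rated safety outcomes

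*Protocol*

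**What the plan says.** Protocol section 11 replaces a formal board with a four-person protocol team; section 7.4 gives the same membership. In routine work the Sponsor's Medical Monitor, "the Investigator and 2 independent physicians, will review blinded pools of AE data at regular intervals". If the count of unexpected AEs is judged significant, a word that the section does not quantify, "the protocol team will be asked to review unblinded safety data in an ad hoc meeting". No member is excepted.

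On enrolment, section 11 says: "The study will not stop enrollment awaiting these reviews". The same paragraph lets the team recommend a temporary or permanent halt to enrolment, a dose reduction, or stopping the study over safety or unblinding concerns.

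The blinding rules allow for this review. Protocol 6.4 lets the blind be broken "if the protocol review committee (Section 11) recommends unblinding data for safety review reasons", and SAP 6.6.3 likewise "if the protocol review committee recommends unblinding data for safety review reasons". Neither limits who may see the data.

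The rating of AEs stays with the Investigator. Protocol Appendix 4 states: "The Investigator will make an assessment of intensity for each AE and SAE reported during the study". The same appendix requires the Investigator to assign causality, and section 7.1 allows the Investigator to end a patient's study medication at discretion. SAP 9.5 compares arms by log-rank test on time to a composite of death, SAE, severe AE, or early termination or withdrawal of treatment.

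**The concern.** A double-blind design protects judged outcomes because the rater does not know the arm. Section 11 keeps that protection for routine reviews by using blinded pools, then drops it for the ad hoc review: the person who rates AEs at the only site is among those who see the unblinded data. There is no second site whose ratings would be untouched, and no text hands later rating to a blinded assessor.

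If an imbalance is seen and the study continues, knowledge of the arm, or a guess at it, could colour whether an event is called severe, serious or related, or whether study medication is stopped. Any such effect would show up as a difference between arms in the composite AE endpoint or in the related-TEAE tables. Describing safety is one of the study's stated aims.

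**Working it through.** The plan states no figure on this point, and no formula gives a bias. The check sets the texts side by side.

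**1. Who sees the data.** Sections 7.4 and 11 name the same four roles. Section 11 sends unblinded data to the team as a whole. Protocol 6.4 and SAP 6.6.3 list this as an exception to keeping the blind until database lock and add no restriction.

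**2. In what form.** No text says by arm or by patient. Both remain possible.

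**3. Which outcomes depend on the Investigator's judgment.**

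| Outcome | Basis | Could blinded judgment be weakened? |
|---|---|---|
| Death | Fact | No |
| SAE by an objective criterion | Appendix 4 | No |
| SAE under the other-situations criterion | Medical or scientific judgment, Appendix 4 | Yes |
| Severe AE | Investigator's intensity grade, Appendix 4 | Yes; it adds to the composite only when the event is not already an SAE |
| Withdrawal for a listed reason | Section 7.1.1 | No |
| Withdrawal at the patient's request | Section 7.1 | No |
| Withdrawal at discretion | Investigator, section 7.1 | Yes |
| Causality | Investigator, Appendix 4 | Yes, but it feeds the related-TEAE tables, not the composite |

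So three judged elements feed the composite, and causality feeds separate tables. The Medical Monitor is given no AE rating. That role's route is narrower: section 8 has safety concerns about continuing a patient's study medication discussed with the Sponsor.

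**4. Which patients.**
- Already randomized and still being assessed: directly exposed, but only if patient-level data are shown. Events graded before the review were graded blind, and Appendix 2 requires changes to source data to be traceable. The endpoint is time to the earliest event, so a patient who already had a component event is settled. Discretionary withdrawal can arise only during dosing, which ends at discharge or Day 29; section 4.3 cites a median stay of 10 to 13 days.
- Not yet randomized: the review cannot show their allocation. The exposure is indirect. If the triggering AEs cluster in one arm, a later patient with the same AE might be guessed to be in that arm.

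**5. What the protocol does elsewhere.** The Schedule of Activities bars the unblinded pharmacist from administering or observing doses. The separation of unblinded knowledge from patient contact is therefore already a principle of this protocol; section 11 does not apply it to the AE rater.

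**The case against.** The strongest case for the plan is that this is a considered trade-off. Section 11 gives reasons for having no formal board: extensive prior exposure, one site, few patients. Under section 7.4 the Sponsor and the Investigator share the decision to discontinue the study, so there is sense in letting them see the evidence. The review is contingent, section 11 itself recognises unblinding as a possible ground for stopping, and protocol 10.1 labels all analyses exploratory. All of this stands and keeps the point modest. It does not explain why the AE rater needs to see unblinded data when two independent physicians are already on the team.

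A reader might infer that, after a review, the Investigator-judged outcomes are no longer blinded at all. The documents do not support that: arm-level tables would not reveal anyone's allocation, and no text says that patient-level data would be shown.

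A reader might also measure the problem by the patients still to be randomized. Reviews come "approximately every 10 patients randomized" and "Approximately 45 randomized patients are planned", so a trigger at the first review would leave 45 − 10 = 35. That is not a measure of size: those are the patients whose allocation the review cannot show directly.

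**Conclusion.** The gap is real and conditional. If the ad hoc review is triggered and the study continues, blinded judgment could be weakened for severe AEs, discretionary withdrawals, SAEs classed as serious by judgment, and causality. The first three feed the composite AE endpoint. The size of any bias cannot be computed from the documents.

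This rests on section 11 being applied as written, with no recusal agreed elsewhere. Two further inferences are not supported:
- That the primary endpoint is compromised. Recovery means being out of hospital, and the rationale for Amendment 3.0 says that the Investigator is not the treating physician. The exposure is at most indirect.
- That an unblinded review took place. The documents do not say.

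The point is a cheap improvement, not a flaw that undermines the trial.

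**What to change.** In protocol section 11, state that if unblinded review is triggered:

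1. Only the two independent physicians see the unblinded data.
2. The Investigator and the Medical Monitor receive only the recommendation.
3. The tables are prepared by someone who already holds the code and makes no AE assessments at the site. The independent statistician who supplies the randomization list (SAP 6.6) would fit. So would the statistical vendor in protocol 6.4, but that vendor is the site's own data management group and would have to be kept separate from the AE assessors.

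Individual emergency unblinding stays as written.

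The SAP shells already show 122 screened and 45 enrolled, so this may come too late to affect conduct. In any case the CSR should state whether an unblinded review took place, who saw what (by arm or by patient), and when. Nothing now secures this. The SAP preface commits to describing deviations from the SAP, and a review held under section 11 would not be one; the planned listings include none for unblinding.

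The cost is protocol wording and one named table preparer. The downside is that two people rather than four weigh the unblinded data, and the Sponsor and Investigator, who share the decision to discontinue the study, act on a recommendation without seeing the data behind it.
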